8.2 Analysis Populations

8.2.1 *Safety Population*

The safety population will consist of all subjects who receive any amount of study drug.

8.3 Demographics and Baseline Characteristics

Demographic and Baseline characteristics (including age, gender, race, weight, height, BMI, Baseline IGF-I level and IGF-I SDS) will be summarized by cohort and for the overall population using descriptive statistics.

Medical history and clinical laboratory tests results will be listed.

Prior and concomitant medications will be summarized by cohort and by the number and percentage of subjects taking each medication.

8.4 Objectives

The primary objective of this study is:

- To evaluate the safety of somavaratan during long-term treatment in adults with GHD

The secondary objectives of this study are:

- To evaluate the dose (starting and maintenance) and the dose titration plan of twice-monthly somavaratan during long-term treatment
- To evaluate the immunogenicity of somavaratan during long-term treatment in adults with GHD by detection and characterization of anti-somavaratan antibodies (anti-drug antibodies, ADAs)

- To evaluate pharmacodynamic responses (IGF-I, IGFBP-3) during long-term somavaratan treatment

Somavaratan ADAs will be summarized descriptively.

8.5 Safety

Safety analyses will be conducted on the safety population and will be summarized by cohort. Safety variables include AEs, clinical laboratory values, vital signs, and physical examination results.

AEs will be coded using MedDRA and will be summarized using the coded terms. Summaries of all treatment emergent adverse events (TEAEs), serious adverse events (SAEs) and Suspected, Unexpected Serious Adverse Reactions (SUSARs) will be presented. The incidence of CTCAE V.4.0 Grade 3 or 4 adverse events will be classified according to severity and relationship to study drug.

Observed and change from Baseline values for laboratory safety panels and vital signs will be summarized using descriptive statistics. Laboratory results will also be summarized and presented as shifts from Baseline.

No formal inferential analyses will be conducted for safety variables.

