Immunogenicity will be assessed by screening for anti-drug antibodies (ADAs) at baseline and every 3 months during the first year and every 6 months thereafter. ADAs will be measured on blood samples collected at troughs (pre-dose). Testing will follow a tiered approach consisting of screening, confirmation, titration, and additional characterization of confirmed ADA positive samples.

STATISTICAL METHODS

Safety data will be listed by subject and summarized by cohort using frequencies or descriptive statistics. All subjects who receive at least one dose of somavaratan will be included in the safety analysis. Summaries of all adverse events (AEs), serious adverse events (SAEs), and incidence of Grade 3 or 4 adverse events will be classified according to severity and relationship to study drug.

No formal hypothesis testing is planned for this extension study.

For continuous variables, descriptive statistics will include the number of subjects, mean, standard deviation (SD), median, minimum, and maximum. For categorical variables, descriptive statistics will include the number and percentage of subjects in each category.

Summaries of subject disposition, demographics, disease characteristics, and exposure and response to dosing of study medication will be provided.

Somavaratan ADAs will be summarized descriptively.

AEs, PK, and PD will also be descriptively summarized by ADA subgroup (positive, negative) to assess potential effects of ADA positivity.

TABLE OF CONTENTS

APPROVAL/SIGNATURE PAGE: SPONSOR AND CONTRACT RESEARCH ORGANIZATION	2
SYNOPSIS: PROTOCOL 15VR8.....	3
LIST OF ABBREVIATIONS AND DEFINITIONS OF TERMS.....	15
1 INTRODUCTION	22
1.1.1 Adult Growth Hormone Deficiency.....	23
1.1.2 Pediatric Growth Hormone Deficiency	24
1.1.3 Summary of Clinical Experience	26
2 STUDY OBJECTIVES.....	28
2.1 Primary Objective.....	28
2.2 Secondary Objectives.....	28
3 INVESTIGATIONAL PLAN.....	29
3.1 Overall Study Design and Plan.....	29
3.2 Rationale for Study Design.....	31
3.3 Dose Selection	31
3.4 Study Duration and Dates.....	32
3.5 Safety Review and Stopping Rules.....	32
3.5.1 Stopping Rules.....	32
STUDY POPULATION SELECTION	33
3.6 Study Population.....	33
3.7 Inclusion Criteria:	33
3.8 Exclusion Criteria:	34
3.9 Subject Withdrawals and Replacements.....	35
4 STUDY TREATMENT(S).....	36
4.1 Description of Treatment(s).....	36
4.1.1 Somavaratan Treatment	36
4.2 Treatments Administered.....	36
4.3 Selection and Timing of Dose for Each Subject.....	37

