Adverse events (AEs) and concomitant medications (CMs) will be captured throughout the study. AEs will be coded using MedDRA dictionary (v 18.0) and summarized using the coded terms; and CMs will be coded using the WHO Drug dictionary (WHODDE [WHO Drug Dictionary Enhanced]). Summaries of all treatment emergent adverse events (TEAEs), serious adverse events (SAEs) and Suspected, Unexpected Serious Adverse Reactions (SUSARs) will be presented. The incidence of Common Terminology Criteria for Adverse Events (v 4.0) Grade 3 or 4 will be classified according to severity and relationship to study drug.

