5.7.3 Severity

AEs will be assessed for severity (intensity) according to the clinical description provided in the CTCAE V.4.0 grading scale (Grade 1, Grade 2, Grade 3, Grade 4, or Grade 5). If an AE cannot be classified using CTCAE V.4.0 terminology, severity will be assessed using the following definitions listed in Table 5.

Table 5 Adverse Event Severity

Grade 1	Mild	Asymptomatic or mild symptoms; clinical or diagnostic observations only; intervention not indicated.
Grade 2	Moderate	Minimal, local, or noninvasive intervention indicated; limiting instrumental activities of daily living. ¹
Grade 3	Severe	Severe or medically significant but not immediately life-threatening; hospitalization or prolongation of hospitalization indicated; disabling; limited self-care activities of daily living. ²
Grade 4	Life-threatening	Life-threatening consequences; urgent intervention indicated.

Grade 5	Death	Death related to the AE.
----------------	--------------	--------------------------

- 1: Examples of instrumental activities of daily living are: using computers, phones, watching TV, reading, etc.
- 2: Examples of self-care activities of daily living are: bathing, dressing and undressing, feeding self, using the toilet, taking medications, etc.

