5.7.7.1 Definition

A serious adverse event (SAE) is defined by federal regulation as any AE occurring at any dose that results in any of the following outcomes: death, life-threatening AE, hospitalization or prolongation of existing hospitalization, a persistent or significant disability/incapacity, or a congenital anomaly/birth defect.

Medically significant events that may not result in death, be life threatening, or require hospitalization may be considered an SAE when, based upon appropriate medical judgment, they may jeopardize the subject and may require medical or surgical intervention to prevent one of the outcomes listed in this definition. Examples of such medical events include allergic bronchospasm requiring intensive treatment in an emergency room or at home, blood dyscrasias or convulsions that do not result in subject hospitalization, or the development of drug dependency or drug abuse.

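### The high-grade adverse event incidence stops at Grade 4, so a subject whose only Grade 3 or higher event is fatal is left out of it

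*Combined protocol and SAP*

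**What the plan says.** Section 5.7.3 has the investigator grade every adverse event on the CTCAE V.4.0 scale, which it lists as "Grade 1, Grade 2, Grade 3, Grade 4, or Grade 5". Table 5 in that section, used where CTCAE has no suitable term, labels Grade 3 severe, Grade 4 life-threatening and Grade 5 death, the last defined as "Death related to the AE".

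The high-grade incidence is described in three places, each with the same upper limit:

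- Section 8.5: "The incidence of CTCAE V.4.0 Grade 3 or 4 adverse events will be classified according to severity and relationship to study drug".
- Section 3.1: "Grade 3 or 4 will be classified according to severity and relationship to study drug".
- Synopsis, Statistical Methods: "incidence of Grade 3 or 4 adverse events will be classified according to severity and relationship to study drug". This is the end of a longer sentence, which places all adverse events and all serious adverse events ahead of the Grade 3 or 4 incidence as items to receive the same classification.

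Section 8.5 also states: "Summaries of all treatment emergent adverse events (TEAEs), serious adverse events (SAEs) and Suspected, Unexpected Serious Adverse Reactions (SUSARs) will be presented". Section 5.7.7.1 lists the outcomes that make an event serious, beginning with "death, life-threatening AE, hospitalization or prolongation of existing hospitalization". No section adds Grade 5 to the high-grade incidence or plans a separate summary of deaths.

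**The concern.** Safety is the primary objective, and the study tests no hypothesis, so the descriptive safety tables are its main result. A reader of a high-grade incidence will normally take it to cover everything from Grade 3 upward. Under the stated limit it does not: a subject with one Grade 4 event is counted, while a subject whose one high-grade event was fatal is not. A summary that falls as the outcome gets worse is a poor description of high-grade toxicity.

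In Sections 3.1 and 8.5 the breakdown by severity and relatedness is attached only to this Grade 3 or 4 item. Read on their own, those two sections do not commit the sponsor to tabulating fatal events by relatedness, although Section 5.7.4 requires the investigator to assess relatedness for every event.

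**Working it through.** The documents give no expected event rate, death rate, power or significance level for this item, so there is no planned figure to reproduce. The check compares the texts and then gives a simple scale for the effect.

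**Step 1. Grades recorded against grades counted.** Recorded (Section 5.7.3): 1, 2, 3, 4, 5. Counted in the high-grade incidence (Synopsis, Sections 3.1 and 8.5): 3, 4. The only grade above the lower cut-off that is left out is Grade 5.

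**Step 2. Which subjects are affected.**

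| Subject's events of Grade 3 or higher | Counted under Grade 3 or 4 | Counted under Grade 3 or higher |
|---|---|---|
| Grade 3 or 4 only | yes | yes |
| A Grade 3 or 4 event and a separate fatal event | yes | yes |
| Fatal event only | **no** | yes |
| One event that worsens from Grade 4 to Grade 5 | depends on a recording rule that is not stated | yes |

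Only the third row is a definite loss.

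**Step 3. Where a fatal event still appears.** Death is a seriousness criterion (Section 5.7.7.1), so a fatal adverse event is a serious one and enters the serious-event summary. If it began after dosing, it also enters the treatment-emergent summary (Sections 5.7.2 and 8.5).

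**Step 4. Whether it appears by severity and relatedness.** Synopsis: yes, because its sentence covers all adverse events and all serious events. Sections 3.1 and 8.5: no commitment, because the treatment-emergent and serious-event summaries are only to be presented, and the breakdown is tied to Grade 3 or 4. The three descriptions do not match.

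**Step 5. Scale.** Let N be the number of subjects dosed (the safety population, Section 8.2.1) and d the number whose only Grade 3 or higher event is fatal.

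Understatement in percentage points = 100 × d / N

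Take N = 250, the enrolment ceiling, and assume all are dosed:

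- d = 0: 0 points
- d = 1: 100 × 1/250 = 0.4 points
- d = 3: 100 × 3/250 = 1.2 points

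The range of 0 to 3 for d is an assumption. Because 250 is a ceiling, 0.4 points is the smallest overall effect per such subject. Within a cohort of n subjects it is 100/n points, and the documents give no planned cohort sizes.

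**The case against.** The strongest reply is that no death is hidden. Fatal events are in the treatment-emergent and serious-event summaries, and the full Synopsis sentence classifies all adverse events and all serious events by severity and relatedness. Under that sentence a fatal event would be shown by grade and by relatedness. Serious events must be reported within 24 hours with the investigator's opinion on causality (Section 5.7.7.2), safety data are listed by subject (Synopsis), and an external monitoring board meets about every six months (Section 3.5). No test or stopping rule uses the Grade 3 or 4 rate. Section 8.1 calls itself a brief summary and leaves the detail to a statistical analysis plan. The text of that detailed plan is not among the documents, and it could still settle the matter.

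All of this stands, and it rules out several stronger readings that a reader might infer:

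- **That deaths go unreported, or are never classified by relatedness.** The serious-event summary and the Synopsis contradict this.
- **That the main severity table is wrong.** The plan gives the Grade 3 or 4 incidence no leading status; it is one item among several. Nor does the plan call it a summary of severe events, and Table 5 keeps the word severe for Grade 3.
- **That an event worsening from Grade 4 to Grade 5 drops out of the count.** This would follow only if each event were recorded once at its highest grade, and the documents state no such rule.

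The reply does not remove the defect in the item itself. The Grade 3 or 4 limit is a stated rule, given three times, rather than a detail left open. The Synopsis breakdown is not carried into Section 8.5, which is the section that governs the safety analysis.

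**Conclusion.** The point holds in a limited form. The high-grade incidence excludes Grade 5, so a subject whose only Grade 3 or higher event is fatal is not counted in it, and Sections 3.1 and 8.5 promise less classification by severity and relatedness than the Synopsis does.

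The effect is small: 0.4 percentage points per such subject if 250 are dosed, 1.2 points for three such subjects, and nothing if there are no deaths. This rests on the enrolment ceiling being reached, on all enrolled subjects being dosed, and on an assumed count of fatal-only subjects. A reader might want to express the loss as a percentage of all subjects with high-grade events. The documents do not support that, since they give no expected number of such subjects. No conclusion of the study depends on the figure. Minor priority, worth correcting because it describes the primary safety objective and is easily put right.

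**What to change.** 1. In the Synopsis, Section 3.1 and Section 8.5, replace the Grade 3 or 4 limit with *Grade 3 or higher (3, 4, 5)*.
2. Show Grade 5 as its own row in that summary.
3. State that each subject is counted once, at the highest grade reached. This also settles how an event that worsens from Grade 4 to Grade 5 is counted.
4. Align Sections 3.1 and 8.5 with the Synopsis, so that all treatment-emergent and all serious adverse events are broken down by severity and relatedness.

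Carry the same wording into the detailed statistical analysis plan before database lock. The cost is text and table layout only: grade and relatedness are already collected for every event, and no extra visits, samples or subjects are needed. The one downside for the sponsor is that the high-grade figure may become slightly less favourable.

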8.6 Retention of Data

All primary data generated in the study and described by Premier, a Contract Research Organization (CRO) (or copies thereof [e.g., laboratory records, data sheets, correspondence, photographs and computer records]), which are a result of the original observations and activities of the clinical study, and are necessary for the reconstruction and evaluation of the study report, will be retained in the Premier archive for a period of 5 years after issue of the final report. At this time, the Sponsor will be contacted to determine whether the data should be returned, retained or destroyed on their behalf. No data will be destroyed without the agreement of the Sponsor.

All study-related records must be retained until 2 years after the last approval of a marketing application in an ICH region and until there are no pending or contemplated marketing applications in an ICH region or at least 2 years have elapsed since the formal discontinuation of clinical development of the investigational product. The Sponsor will inform the Investigator/Institution when the documents no longer need to be retained. The Investigator must obtain approval in writing from the Sponsor prior to destruction of any records. Typically, these records will be held in the Investigator's archives. If the Investigator is unable to meet this obligation, the Investigator must obtain permission from the Sponsor to make alternative arrangements. Details of these arrangements must be documented in writing to the Sponsor.

Specimens requiring frozen storage are specifically excluded from the above. These will be retained for as long as the quality of the material permits evaluation but for no longer than 6 months after completion of the study (defined as issuance of Clinical Study Report). The Sponsor will be notified of the intent to destroy samples and any financial implications before specimens are destroyed on their behalf.

8.7 Interim Analysis

No formal Interim analysis is planned however data from this study may be analyzed periodically to assess the dosing regimen and allow adjustments to alleviate safety concerns or optimize normalization of IGF-I SDS responses.

9 ADMINISTRATIVE CONSIDERATIONS

9.1 Investigators and Study Administrative Structure

The Sponsor has an agreement with Premier Research (Premier), a CRO, to provide project management oversight for this protocol. Premier has been assigned many study oversight responsibilities for the protocol conduct. A formal transfer of obligations document outlines the activities assigned to Premier.

9.2 Institutional Review Board (IRB) or Independent Ethics Committee (IEC) Approval

The Investigator will initiate and enroll subjects only after IRB/IEC approval of the protocol and the informed consent documents have been received. All recruiting materials used in the study must have IRB/IEC approval. Progress reports regarding the study will be submitted to the IRB/IEC in accordance with institutional and regulatory guidelines.

9.3 Ethical Conduct of the Study

The study will be performed in compliance with the FDA CFR for GCP and ICH Regulations. These procedures ensure the protection of the rights and the integrity of the subjects, adequate and correct conduct of all study procedures, adequate data collection, adequate documentation and adequate data verification. The Standard Operating Procedures (SOPs) relevant in the context of the study are available at Premier.

9.4 Subject Information and Consent

Before being enrolled, subjects must provide informed consent to participate after the nature, scope, and possible consequences of the study have been explained in a form understandable to them. The Investigator will not undertake any measures specifically required only for the clinical study until valid consent has been obtained. A copy of the consent document must be given to the subject. The original signed consent document will be retained by the Investigator.

9.5 Subject Confidentiality

Subject confidentiality will be maintained throughout the study according to applicable guidelines, regulations and IRB requirements. All samples, study clinical data, and reports of results will de-identify individual subjects. Subjects will be identified by initials (where allowed), date of birth, gender and subject number only for use in data collection. Published data will provide subject numbers only if needed for clarity of presentation (e.g., in individual event listings).

9.6 Study Monitoring

All investigational sites will receive on site visits from the Sponsor and/or Sponsor designee, Premier. Site visits may be conducted with representatives from both the Sponsor and Premier in attendance. All sites will receive at a minimum a pre-study qualification visit and a site initiation visit. All sites that enroll subjects into the study will receive routine monitoring visits where source data verification will be conducted by the monitor.

All activated sites will receive study close-out visits by the Study Monitor upon closure of the study.

Premier will develop a monitoring plan that will be approved by the Sponsor and followed for the duration of the study. All study sites must allow direct access to all pertinent study documentation and medical records for enrolled subjects.

9.7 Case Report Forms and Study Records

Source documents must be maintained for each subject during the course of the study. The documents must demonstrate in writing that informed consent was obtained prior to subject participation. Source documents include the signed original informed consent forms (ICFs), medical records including physician notes, nursing flow sheets, and hospital charts. They include documentation of all procedures conducted for the study and are the primary original source for all study data except where otherwise specified.

Electronic Case Report Forms (eCRFs) will be used in this study and must be completed for each enrolled subject.

All protocol-required information collected during the study must be entered by the Investigator or the designee in the eCRF. eCRF completion and correction will be performed in accordance with the study eCRF guidelines.

The Investigator or designee should complete the eCRF pages as soon as possible after the study information is obtained. An explanation should be given for all missing data.

The completed eCRF must be reviewed and signed by the Principal Investigator.

9.8 Protocol Violations/Deviations

Protocol-specified events, visits, tests, and procedures should be followed without exception. In situations where protocol deviations (e.g., missed visits or tests) occur due to unforeseen circumstances, documentation of the reason should be made in the source document and documented by the CRA for inclusion in the Clinical Study Report (CSR).

9.9 Access to Source Documentation

All study data entered into the electronic CRF must be verifiable to the source data. The Sponsor and its delegated representative study monitors and auditors must have access to all original recordings, laboratory reports and enrolled subject's medical records.

9.10 Data Generation and Analysis

Premier (the CRO) will perform the data analysis. The results of the study will be reported together in one clinical study report. A detailed Statistical Analysis Plan describing the methodology to be used will be finalized prior to study enrollment and may be modified as needed and documented prior to database lock.

Premier and the Sponsor will prepare an integrated clinical, pharmacodynamic and pharmacokinetic report. Prior to issuing the final CSR, Premier will prepare a draft report for approval by the Sponsor. The report will be in accordance with the ICH note for Guidance on Structure and Content of CSRs. The draft report may be submitted for Quality Assurance audit, the findings of which will be incorporated into the final version.

9.11 Financial Disclosure

A completed financial disclosure document is required for all Investigators participating in this study.

9.12 Publication and Disclosure Policy

The Sponsor holds all publication rights to the aggregate data obtained from this study. Study Investigators will submit any planned publication of individual site data to Sponsor for review and approval at least 60 days prior to submission to the publisher.

